## 5. Inclusion/Exclusion Criteria

Inclusion criteria: In order to be eligible to participate in this study, an individual must meet all of the following criteria:

1. Provision of signed and dated informed consent form
2. Stated willingness to comply with all study procedures and availability for the duration of the study
3. Self-reported expectant father and pregnant partner (expectant mother)
4. Aged  $\geq 18$  years
5. In a romantic relationship and expect to continue to be in this relationship during the study period
6. Willingness to adhere to the Text4Father regimen (for fathers)
7. English speakers only: The Text4Father content was not developed for use with non-English speakers or hearing-impaired individuals. Therefore, non-English speakers and hearing-impaired individuals will not be included.
8. Lower socioeconomic status (SES) (e.g., less than a 4-year college degree, or vocational/trade school or less, or qualify for Medicaid/public insurance)
9. Access to necessary resources for participating in a technology-based intervention (i.e., cell phone) and willing/able to receive/send texts

Exclusion criteria: An individual who meets any of the following criteria will be excluded from participation in this study:

1. Individuals who are not able to provide informed consent.

## 6. Drugs/ Substances/ Devices

a. The rationale for choosing the drug and dose or for choosing the device to be used.  
Not applicable

b. Justification and safety information if FDA approved drugs will be administered for non-FDA approved indications or if doses or routes of administration or participant populations are changed.

Not applicable

c. Justification and safety information if non-FDA approved drugs without an IND will be administered.

Not applicable

## 7. Study Statistics

Name	Parenting Sense of Competence (PSOC)
Type	Primary
Time Frame	Baseline; post-treatment at follow-up
Brief Description	Measures parents' perceived confidence (self-efficacy) with overall parenting and parenting skills

Name	Technology usability
Type	Other
Time Frame	Post-treatment at follow-up
Brief Description	Assesses technology usability among participants assigned to the intervention
Name	Technology acceptance
Type	Other
Time Frame	Post-treatment at follow-up
Brief Description	Assesses technology acceptance among participants assigned to the intervention

a. Statistical plan including sample size justification and interim data analysis.

**Number of subjects expected to enroll:** Total of N=240 (120 fathers; 120 mothers) or 60 couples per group (treatment, and standard of care control).

**Expected effect size:** Moderate effect size (i.e.,  $d \geq 0.472$ ).

**Power.** We evaluated power for the fixed effects in a hierarchical linear model including four discrete covariates to consider the average rate of change in paternal parenting constructs due to the intervention over duration of the study time period. With a sample size of N=60 participants per study arm, we will have 80% power to detect moderate effect size (i.e.,  $d \geq 0.472$ ) in outcomes. This power calculation also accounts for study attrition (anticipated at 20% loss to follow-up over the 7-month study period). We used one of the few studies that evaluated changes in parenting constructs comparing treatment for father engagement to a control group only at the end of treatment to inform these calculations and expected effect size. This study found treatment fathers had 12.7% higher paternal infant engagement at the end of the treatment compared to the control group; and parenting self-efficacy was 6.2% higher in treatment than in control group participants.

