### Statistical methods

**Aims 1 and 2. Feasibility and Acceptability.** Using completed clinic appointment, screener, and consent data, we will assess feasibility of overall recruitment by calculating the proportion of eligible fathers who consent to study participation and recruitment by resident status. Based on our pilot work, we anticipate recruiting  $\geq 70\%$  of fathers who are approached. We will calculate feasibility of retention as the proportion of enrolled participants who complete 7-month follow-up survey (2-months of postnatal age). We will calculate study retention overall and separately by treatment assignment and use Chi-square tests to determine if we achieved follow-up of  $\geq 80\%$  by treatment assignment.

In the Text4Father arm, we will calculate the proportion of individuals completing the

intervention and assess at exit these participants' technology usability (12 items), acceptance (8 items), and satisfaction (1 item) (on 5-point scales from "strongly disagree" to "strongly agree"). We will examine whether we achieved  $\geq 75\%$  agree/strongly agree usability/acceptability rates and generate means (SD) for each.

**Aim 3. Efficacy.** We will examine the effect of the randomization scheme and explore missing data due to survey non-response and attrition. We will then apply separate random intercept coefficient regression models for each study outcome accounting for two levels of nesting (repeated measures and individuals). Each model will estimate differences among intervention and usual care control arms identifying change in each study outcome between baseline and follow-up. This type of analysis will allow for examining 1) within-individual change over time in an outcome, accounting for dependency among observations within individuals by modeling within-person error, 2) between-individual variation over time, and 3) between-subjects effects based on group assignment to identify significant differences in content (Text4Father) as compared to usual care. Our sample size should be large enough to adequately power analyses for examining change in fathers' engagement (see below). The fixed effects from these analyses will help determine the expected effect size for other outcomes to inform power calculations for a larger R01-funded trial.

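### The 80% power at d = 0.472 is not shown to hold for secondary outcomes that exist only after birth, and the Aim 3 change model cannot be fitted to them as written

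*Combined protocol and SAP*

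**What the plan says.** **Power (section 7, a).** "With a sample size of N=60 participants per study arm, we will have 80% power to detect moderate effect size", namely d of at least 0.472, in outcomes without further limit. The calculation is said to allow for 20% loss over 7 months. Section 4 (Participants and Recruitment) sets a target of 48 dyads with complete data out of 60, and the Data Sharing Plan expects 96 respondents at follow-up, so 48 per arm is the analysed number. Power was evaluated in a "hierarchical linear model including four discrete covariates", "to consider the average rate of change in paternal parenting constructs due to the intervention". The effect size is informed by a cited study, of which the plan reports: "This study found treatment fathers had 12.7% higher paternal infant engagement at the end of the treatment compared to the control group". Alpha, sidedness, the SD behind d, the baseline to follow-up correlation, and the names and strength of the covariates are not given.

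**Aim 3 (Statistical methods).** A separate random-intercept model, with repeated measures nested in individuals, is planned for each outcome: "Each model will estimate differences among intervention and usual care control arms identifying change in each study outcome between baseline and follow-up". No covariates are named. The same paragraph adds: "Our sample size should be large enough to adequately power analyses for examining change in" fathers' engagement.

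**Timing and outcomes.** Enrolment closes at 25 weeks' gestation, and the only follow-up survey is about 2 months after birth. The Measures Table lists infant engagement, time spent with the infant and safe sleep care as secondary outcomes. The Conceptual Framework text places these behaviours at follow-up.

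**The concern.** A power figure stated for outcomes in general, together with a sentence naming engagement, tells the reader that infant-care engagement is covered at 80%. But a father cannot report hours with his infant, sleep practices or infant-care activities before the birth. With one observation per father there is no change to model, and a random intercept cannot be separated from residual error. Any precision that the power calculation took from repeated measurement is not available for these outcomes.

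The primary objective includes generating effect sizes for a larger trial. Readers of the results need to know which outcomes the 80% covers, so that a null result on engagement is not read as coming from a comparison with a 20% chance of missing d = 0.472.

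**Working it through.** **Inputs.** From the plan: d = 0.472, 60 enrolled per arm, 20% loss, so 60 × 0.8 = 48 completers per arm. Assumed, because not stated: alpha 0.05 (both one- and two-sided shown) and d in units of the follow-up SD.

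**1. Trying to reproduce the 80% from the stated inputs.** For two means with n per arm, the noncentrality is d × √(n/2) on 2n − 2 degrees of freedom.

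| Completers per arm | Noncentrality | Two-sided | One-sided |
|---|---|---|---|
| 48 | 0.472 × √24 = 2.312 | 62.9% | 74.2% |
| 60 (no loss) | 0.472 × √30 = 2.585 | 72.7% | 82.3% |

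None of these is 80%. The only cell above it ignores the attrition that the plan says is included. The plan's figure must therefore rest on inputs it does not state: a baseline correlation, covariate strength or another scale for d.

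**2. Outcomes seen only after birth.** The first row of the table applies directly. The chance of missing a true d of 0.472 is 100 − 62.9 = 37% two-sided or 100 − 74.2 = 26% one-sided, against 20% as stated. The difference detectable with 80% power is 0.578 SD two-sided or 0.511 SD one-sided. Unadjusted, 80% at 0.472 would take 72 completers per arm two-sided or 57 one-sided.

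**3. What the four covariates would have to do.** With residual variance 1 − R² and 90 degrees of freedom:

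- R² of 0.10 gives 67% two-sided and 78% one-sided.
- R² of 0.20 gives 73% and 82%.
- 80% is reached at R² of about 0.33 two-sided or 0.15 one-sided.

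**4. Prenatal involvement as a single covariate.** With residual variance 1 − r² and 93 degrees of freedom:

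- r = 0.3, 0.4, 0.5 and 0.6 give 67%, 70%, 75% and 82% two-sided.
- The same values give 78%, 80%, 84% and 89% one-sided.
- 80% needs r of about 0.58 two-sided or 0.38 one-sided.

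**5. Outcomes measured at both times, PSOC included.** Take d in raw-score SD units, with 60 baselines and 48 follow-ups per arm. When each arm has its own baseline mean, the arm-by-time estimate has variance 2[(1 − ρ)²/60 + (1 − ρ²)/48].

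- At ρ = 0.5: 2(0.25/60 + 0.75/48) = 0.0396, and two-sided power is 65%.
- At ρ = 0.3, 0.6 and 0.7: 52%, 74% and 85%.
- 80% needs ρ of about 0.65 two-sided or 0.55 one-sided.

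With a common baseline mean or ANCOVA, the variance is 2(1 − ρ²)/48, and the ρ needed two-sided falls to about 0.56 (normal approximation) or 0.58 (t); one-sided it is about 0.37 or 0.38. Aim 3 does not say which form is meant.

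**The case against.** **Baseline behaviour is collected.** The Schedule of Activities marks a behaviour survey at the first visit. The Surveys text covers involvement in pregnancy, the mothers' survey lists partner engagement in infant care at baseline, and the data description counts behavioural engagement among baseline and follow-up data. This shows that something is asked before birth. It cannot be the same quantity as care of a born infant, so it does not yield a change score, though it could serve as a covariate. The instruments are not in the documents. Injury prevention is listed with these behaviours, but some of its items might be answerable before birth, so the point does not rely on it.

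**The power model has covariates.** This stands as a limit. One-sided, an R² of about 0.15 would be enough. Hence the right conclusion is that 80% is not shown, and a reader who infers that it is proved false goes further than the documents allow. Still, Aim 3 names no covariates and no R² is given.

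**The power paragraph concerns change in parenting constructs, and the only efficacy outcome tabulated in section 7 is PSOC, which has a baseline.** Fathers' engagement may also be meant broadly. Both points are fair. But the figure is given for outcomes without limit, an infant-engagement result informs the effect size, and Aim 3 claims adequate power for engagement.

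**A reader might infer that the primary outcomes are underpowered.** The documents do not support that: correlations of roughly 0.56 to 0.65 would deliver 80% two-sided, and no correlation is stated against which to judge.

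**The study is preliminary.** These outcomes are secondary, and no decision is tied to significance. That limits the consequence but does not correct the statement.

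**Conclusion.** The point holds in limited form. For infant-care engagement, time with the infant and safe sleep, the planned change model cannot be fitted as written and becomes a comparison at follow-up. On alpha 0.05, d in follow-up SD units and no covariates, power at 0.472 is about 63% two-sided or 74% one-sided rather than 80%. These figures move with the assumptions; if d was defined on another scale, such as the SD of change, they are not directly comparable with the plan's figure. For outcomes with a baseline, the finding is only that the 80% cannot be checked. The importance is moderate: the power statement and the Aim 3 rule should be corrected, while the design and conduct of the trial are unaffected.

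**What to change.** Do not enrol more fathers. Change the text in three places.

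1. **Power paragraph.** Limit the 80% to outcomes measured twice and complete its inputs, for example:

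> For outcomes measured at both baseline and follow-up, 48 completers per arm (60 enrolled, 20% loss) give 80% power at d = 0.472, assuming [alpha, sidedness], d in units of [SD], a baseline to follow-up correlation of [value], [arm-specific or common] baseline means and [covariates]. Outcomes that exist only after birth are compared at follow-up; with the same alpha and covariates the detectable difference is [value] SD.

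   If that comparison is unadjusted at alpha 0.05, the last value is about 0.58 two-sided or 0.51 one-sided.

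2. **Aim 3 model.** State that post-birth-only outcomes are compared between arms at follow-up, adjusted for the same covariates as the power model and, if the team wants it, for prenatal involvement. Name the covariates, and list which outcomes have a true baseline.

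3. **Aim 3 engagement sentence.** Qualify it to match the revised power paragraph.

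The cost is a reworded paragraph and a few sentences in Aim 3, with no added participants or data collection. The downside is a less favourable stated figure for these secondary outcomes.

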### Statistical methods

**Aims 1 and 2. Feasibility and Acceptability.** Using completed clinic appointment, screener, and consent data, we will assess feasibility of overall recruitment by calculating the proportion of eligible fathers who consent to study participation and recruitment by resident status. Based on our pilot work, we anticipate recruiting  $\geq 70\%$  of fathers who are approached. We will calculate feasibility of retention as the proportion of enrolled participants who complete 7-month follow-up survey (2-months of postnatal age). We will calculate study retention overall and separately by treatment assignment and use Chi-square tests to determine if we achieved follow-up of  $\geq 80\%$  by treatment assignment.

In the Text4Father arm, we will calculate the proportion of individuals completing the

intervention and assess at exit these participants' technology usability (12 items), acceptance (8 items), and satisfaction (1 item) (on 5-point scales from "strongly disagree" to "strongly agree"). We will examine whether we achieved  $\geq 75\%$  agree/strongly agree usability/acceptability rates and generate means (SD) for each.

**Aim 3. Efficacy.** We will examine the effect of the randomization scheme and explore missing data due to survey non-response and attrition. We will then apply separate random intercept coefficient regression models for each study outcome accounting for two levels of nesting (repeated measures and individuals). Each model will estimate differences among intervention and usual care control arms identifying change in each study outcome between baseline and follow-up. This type of analysis will allow for examining 1) within-individual change over time in an outcome, accounting for dependency among observations within individuals by modeling within-person error, 2) between-individual variation over time, and 3) between-subjects effects based on group assignment to identify significant differences in content (Text4Father) as compared to usual care. Our sample size should be large enough to adequately power analyses for examining change in fathers' engagement (see below). The fixed effects from these analyses will help determine the expected effect size for other outcomes to inform power calculations for a larger R01-funded trial.

**Exploring moderating factors.** We will explore the moderating effect of fathers' resident status, partner relationship quality, and caregiver conflict from perspectives of both parents on the study's outcomes given that each of these may influence fathers' access and experience with infant engagement, as well as other background factors. These findings will inform sampling decisions and future research questions for a larger trial. We will also explore how infant sex as a biological variable might impact father engagement; however, this is not supported by past work in this area.

We will also explore differences among intervention and usual care control arms for each maternal and infant outcome between baseline and follow-up.

b. Early stopping rules.

This study may be stopped prior to its completion if:

- (1) participants experience (adverse events) AEs or severe AEs (SAEs) that are felt to be related to study participation, at which point consideration will be given to temporarily or permanently suspending study activities and/or enrollment. This decision would be made in consultation with the study's IRB and sponsor (NICHD);
- (2) difficulty in study recruitment or retention will significantly impact the ability to evaluate the study endpoints. The investigators will consult with the study monitors to assess the impact of significant data loss due to problems in recruitment, retention, or data collection;
- (3) any new information becomes available during the trial that necessitates stopping the trial; or
- (4) other situations occur that might warrant stopping the trial.

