**Figure 1. Overview of Study Procedures**

**Table 1. Schedule of Activities**

	pre-screening Pre- consent)	(Visit 1/ Time 1)	(Visit 2/ 2 months)	(Visit 2/ 4 months)	(Visit 3/ 6 months)	(Visit 2/ Time 2/ 7 months+/ weeks)
Review eligibility (phone/in-person)	X					
Informed consent (phone/in-person)		X				
Demographics/background characteristics		X				
Outcome evaluation						
Parent knowledge, self-efficacy, behavior survey		X				X
Intervention acceptability survey						X
Monitoring responsive texts			X	X	X	
Randomization		X				
Control & Experimental Interventions – Text4Father		X	X	X	X	
Adverse Events Reporting		X	X	X	X	X

**Setting.** We will conduct this study and recruit participants in Baltimore. Baltimore is a community with marked health disparities related to maternal and infant outcomes. In 2015 in Baltimore, the infant mortality rate was almost 2 times higher for black (9.7/1,000 live births) than white infants (5.4/1,000); this rate was 1.3 times greater than Maryland's rate, and 12% of babies born were low birthweight versus a national average of 8%. Settings will include the Hopkins Maternal-Fetal Medicine (MFM) Clinic and Fetal Assessment Center where we successfully collaborated for the 6-week feasibility pilot that informs this proposal. [name], Professor and Director of the Johns Hopkins' Division of MFM, facilitated MFM staff education for the pilot and is committed to ensuring this project's feasibility. The Center sees over 21,000 fetal ultrasound exams and delivers over 2,400 babies each year. The majority of patients are publicly insured (62%) and half are African American. Based on our preliminary work, we estimate that 865 infants each year will have first-time lower income fathers.

**Participants and Recruitment.** Research staff will recruit 120 adult expectant fathers and their female partners (120 pregnant females) (60 dyads per study arm) from the Hopkins' MFM Clinic and Fetal Assessment Center to be enrolled through 25 weeks gestation. The index participant and their partner will contact study staff to be scheduled for a research visit. An eligibility screener will be individually completed with both members of the dyad to determine study eligibility. Our target is to have complete data on 48 dyads so we set sample size at 60 in order to account for attrition.

[figure not shown]

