We will use the following recruitment strategy: 1) upon entry into prenatal care, pregnant women will receive informational study flyers to contact study staff for participation and referral of their male partners; 2) we will actively recruit at prenatal and ultrasound visits since many fathers accompany their partners to these visits and clinic staff will call prior to appointments to share study information, assess interest, and if interested share to have father join them at their appointment when they can complete study procedures; and 3) we will recruit unaccompanied pregnant women and get permission to recruit their male partners. We will build on established relationships with other metro Baltimore MFM settings if we need other settings for this trial. We will also plan to disseminate study flyers and posters to post and distribute at other locations, such as adult outpatient settings, WIC, home visiting programs for pregnant and parenting families, and other OB settings, share existing recruitment materials (e.g., study flyer) via website posting, and social media (e.g., Facebook). We will also inform interested participants that they can refer other individuals to the study.

**Enrollment, and Consent.** Recruiters will be available via phone during office and some evening hours for participant recruitment. Providers will refer eligible participants or expectant parents can contact study staff directly. Individuals who agree to be contacted will be approached by a recruiter in person or via phone and an eligibility screener will be individually completed with both members of the dyad to

determine study eligibility. If eligible, they will complete oral informed consent and intervention procedures. The index patient and partner will be consented individually. At enrollment, the research staff will perform a detailed review of the Text4Father study with informed consent, and collect baseline measures. Completion of informed consent will be documented in RedCap by study staff at the time of enrollment and online questionnaire will be automatically uploaded to a secure server for warehousing in a central database. This study will not involve linkage to medical records.

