### **Quality Control**

**1. Quality Control-Treatment Fidelity.** Drs. [name], [name], and [name] will train and supervise research staff to ensure appropriate protocol execution. Research staff will activate Text4Father for consented participants randomly assigned to the intervention. [name] will continually monitor and document fidelity via: 1) Technical functionality (Does technology operate as intended?) assessed by confirming that the system sends the welcome text and is received by participants at enrollment; 2) Technical stability (Does technology consistently operate as intended?) assessed by ensuring texts are consistently delivered as intended with minimum system failures/bounce backs. At the follow-up visit, study staff will ask participants assigned to the intervention arm to verify text receipt as well as to record unread texts. Study staff will ask them to open their phone to view the number of unread texts and then record the number of unread texts from Text4Father. If no texts are present, they will be asked why the texts were deleted. Study staff will also record texts that were received to ensure technical stability. The study team will also ensure 3) Technical quality assessed by keeping content up-to-date.

**2. Recruitment Screener.** Includes collection of basic demographic data and the outcome of recruitment effort so that we can keep an accurate account of referral patients who are ineligible and/or refuse to participate in the intervention.

**3. Surveys.** We developed a survey to collect information about fathers' knowledge, self-efficacy, and behavioral engagement in parenting and infant care, as well as technology acceptability.

From fathers, we will collect self-report responses about their background sociodemographic factors, including use of other pregnancy/parenting/infant care resources, perceptions of caregiver conflict, and about their infant, as well as their knowledge, self-efficacy, beliefs, and behaviors related to involvement in pregnancy and with their infant, cooperative coparenting, and relationship quality with partner and personal health behaviors, using a survey instrument at baseline and at 2 months of postnatal age (7-month follow-up) in-person, via phone, or electronically via Qualtrics. At follow-up (7-months), we will also assess intervention fathers on technology usability, acceptability, and satisfaction. This survey takes about 40-45 minutes to complete.

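### Chi-square tests are given the job of deciding whether 80% follow-up was reached in each arm, but a non-significant result would not show that it was; the recruitment rate and its anticipated 70% also use different denominators.

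*Combined protocol and SAP*

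**What the plan says.** **Retention.** Section 7 (Statistical methods, Aims 1 and 2) defines retention as "the proportion of enrolled participants who complete 7-month follow-up survey" and continues: "We will calculate study retention overall and separately by treatment assignment and use Chi-square tests to determine if we achieved follow-up of" at least 80% by treatment assignment. It gives no null value, significance level, form of chi-square test or confidence interval.

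The 80% comes from the sample size. Section 4 (Participants and Recruitment) plans 60 dyads per arm and says: "Our target is to have complete data on 48 dyads so we set sample size at 60 in order to account for attrition". The Power paragraph of section 7 anticipates 20% loss over the 7 months.

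**Recruitment.** The same paragraph of section 7 measures recruitment by "calculating the proportion of eligible fathers who consent to study participation". The next sentence anticipates, from pilot work, at least 70% "of fathers who are approached". Section 4 (Enrollment, and Consent) puts the approach before the screening: people who agree to contact "will be approached by a recruiter in person or via phone and an eligibility screener will be individually completed". Section 4 (Quality Control, Recruitment Screener) says that the screener serves to "keep an accurate account of referral patients who are ineligible and/or refuse to participate".

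**The concern.** Whether follow-up reached 80% is a question about each arm's proportion against a fixed figure. As written, the answer comes from a significance test. The test most readers would understand by a chi-square by treatment assignment compares the arms with each other, which is a different question. The other candidate, a one-sample test against 80%, does address the right figure. With 60 per arm, though, a non-significant result is compatible with having clearly missed the target.

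Recruitment and retention are the named evidence for the first secondary objective, feasibility is part of the primary objective, and the results are meant to inform a larger trial. At stake is a feasibility statement that could disagree with the proportions printed beside it, and a recruitment rate that cannot be set directly against the figure it is meant to be compared with.

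**Working it through.** **Inputs.** 60 dyads per arm, 120 in all (section 4, Participants and Recruitment; section 7, number of subjects). Target of 48 complete dyads out of 60 (section 4). Loss of 20% (section 7, Power). The documents state no significance level for this test, so two-sided 0.05 is assumed.

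**1. The plan's own figure.** 48 / (1 − 0.20) = 60 per arm, as stated. So 80% means 48/60 per arm and 0.80 × 120 = 96/120 overall.

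**2. Between-arm chi-square.** For counts a, b (arm 1: complete, lost) and c, d (arm 2), with total N = 120, X² = N(ad − bc)² / (product of the four margins). The continuity correction replaces |ad − bc| by |ad − bc| − N/2.

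- 42/60 v 42/60: ad − bc = 0, X² = 0, p = 1.0. Both arms are at 70% and miss the target.
- 57/60 v 48/60: ad − bc = 57×12 − 3×48 = 540. X² = 120 × 540² / (60 × 60 × 105 × 15) = 6.17, p = 0.013. Corrected: 120 × 480² / 5,670,000 = 4.88, p = 0.027. Both arms meet the target.
- 50/60 v 44/60: ad − bc = 50×16 − 10×44 = 360. X² = 120 × 360² / (60 × 60 × 94 × 26) = 1.77, p = 0.18 (corrected 0.27). One arm meets the target and one misses it.

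The p-value does not follow the 80% target in any of the three cases.

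**3. One-sample chi-square against 80%.** The expected counts are 48 and 12, so X² = (x − 48)²/48 + (x − 48)²/12 = (x − 48)² × 5/48.

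- x = 42 or 54: 36 × 5/48 = 3.75, p = 0.053.
- x = 41 or 55: 49 × 5/48 = 5.10, p = 0.024.

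Every count from 42/60 (70%) to 54/60 (90%) is therefore non-significant. That range holds six counts that miss the target (42 to 47) and seven that meet it (48 to 54). From the binomial distribution, an arm whose true retention is 70% falls in 42 to 47 with probability 0.51: it misses the target and is not rejected. A one-sided exact test for a shortfall rejects 42/60 (p = 0.043) but not 43/60 to 47/60 (p = 0.077 to 0.42). A one-sided exact test for exceeding 80% needs 54/60 (p = 0.031; 53/60 gives 0.067).

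**4. What the observed proportion gives.** Exact (Clopper–Pearson) 95% limits are the 2.5% point of Beta(x, n − x + 1) and the 97.5% point of Beta(x + 1, n − x). For 48/60 they are 67.7% to 89.2%; for 96/120, 71.7% to 86.7%.

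**5. Unit.** Retention is defined on enrolled participants, of whom there are 240, while the target is in dyads. These can differ. If 80% of fathers and 80% of mothers complete, complete dyads lie between 1 − 0.20 − 0.20 = 60% (losses never in the same couple) and 80% (losses always in the same couple).

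**6. Recruitment.** If every father approached is screened, the rate among approached equals the rate among eligible times the share of approached found eligible. The documents do not give that share. Over an assumed range of 70% to 100%, a rate of 70% among eligible corresponds to 0.70 × 0.70 = 49% up to 0.70 × 1.00 = 70% among approached. This illustrates the direction only. Fathers who decline before screening have unknown eligibility and fall outside the formula.

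**The case against.** The strongest reply is that the sentence probably compresses two sensible intentions: read the proportions against 80%, and compare the arms for differential attrition. The plan does commit to reporting retention overall and by arm, so a shortfall would be visible whatever the test said. That stands, and it limits the consequence. It does not rescue the sentence, which gives the decision to the test.

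A reader might go further and infer that no chi-square test could bear on the 80% figure. The documents do not support that. The form is not stated, and a one-sample test that rejects is informative: 55/60 gives p = 0.024 in the upward direction. The fault lies in what a non-significant result would be taken to mean, and in the between-arm form.

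A reader might also infer that a decision about the larger trial would go wrong. No go/no-go rule is tied to this test, and section 7(b) handles recruitment and retention problems by consultation with the study monitors.

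On recruitment, the 70% is what the investigators anticipate, not a criterion. Section 4 says "Providers will refer eligible participants or expectant parents can contact study staff directly", so for referred fathers the approached and the eligible may largely coincide. The pilot's own denominator is not given. All of this stands, so the documents do not show that recruitment would be overstated, or by how much. What remains is that two adjacent sentences use different denominators.

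**Conclusion.** The point holds in limited form. As a rule for deciding whether 80% follow-up was achieved, the chi-square does not work. The between-arm test answers another question, and the one-sample test cannot separate 70% from 90% at 60 per arm. The between-arm examples are worked with counts chosen for illustration. The range from 42/60 to 54/60 rests on the assumed two-sided alpha of 0.05.

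The effect is confined to how feasibility is stated. The sample size and the efficacy analysis do not depend on it.

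The recruitment mismatch is secondary: the denominators differ as written, and the size of any resulting gap cannot be derived from the documents.

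**What to change.** **Retention.** Replace the test with the observed proportion and an exact 95% CI, overall and per arm, read against 96/120 and 48/60. Name complete dyads as the deciding unit, since section 4 sets the target in dyads, and show fathers and mothers separately as description. Keep the between-arm chi-square, labelled as a check for differential attrition only.

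**Recruitment.** Put the statistic and the 70% on one denominator. Either report the rate among fathers approached beside the rate among eligible fathers, where approaches are logged, or reword the 70% if the pilot figure was computed among eligible fathers. Show people who contact the study themselves separately, since they were not approached in the same sense.

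**Cost.** One paragraph is reworded; sample size and follow-up do not change. The retention figures need no new data. The rate among fathers approached may need a simple log: the screener is described as accounting for referrals who are ineligible or refuse, and does not clearly cover fathers who decline before screening.

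The observed proportion is also noisy. At a true 80%, one arm shows at least 48/60 with probability 0.58, both arms with 0.576² = 0.33 if independent, and the pooled figure reaches 96/120 with probability 0.55. At a true 70%, one arm reaches 48/60 with probability 0.06. The interval should therefore always stand beside the proportion.
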